## **L. Subgroups of Analysis Populations**

No subgroup analyses are planned.

## **M. Data Display Characteristics**

Data displays produced for this study will include three types – summary tables, data listings, and figures. Summary tables and figures will be produced as specified in the following section. Data listings will list the data recorded on the electronic case report form (eCRF) as defined in Study Data Tabulation Model (SDTM) or derived for each subject. Additional data listings will be produced for outcome measures that involve extensive procedures to derive the analyzed outcomes. Unless otherwise specified, listings will be ordered by treatment, cohort, subject number, and date/time of assessment. Data listings will not display subject initials.

Subjects who received placebo will be combined into one treatment group for purposes of analysis. Therefore, the treatment groups will be the following (as applicable depending on the open cohorts):

- JK07 0.03 mg/kg
- JK07 0.09 mg/kg
- JK07 0.27 mg/kg
- JK07 0.54 mg/kg
- JK07 1.08 mg/kg
- Placebo (corresponding to the pooled group of subjects receiving the placebo)

The PK and exploratory PD analyses will be performed at CR Medicon, and the other analyses will be performed by qualified IQVIA Biotech statisticians and SAS programmers. SAS 9.4 or higher (SAS Institute, Inc., Cary, North Carolina) will be employed for all the statistical analyses.

Pharmacokinetic parameters will be derived using standard non-compartmental analysis (NCA) methods with Phoenix WinNonlin® Version 8.0 (Certara, L.P. Princeton, New Jersey, United States of America [USA]) at Nanjing CR Medicon Pharmaceutical Technology Co., Ltd.

Summary tables will display descriptive summary statistics calculated for each of the treatment groups, unless described otherwise in following sections. Results will be summarized by treatment and overall, where appropriate.

The following descriptive statistics will be used when applicable to summarize the data unless otherwise specified:

- Continuous variables: number of non-missing observations (n), arithmetic mean (mean), standard deviation (SD), median, minimum (min) and maximum (max)
- PK concentrations and parameters: coefficient of variation (%CV), geometric mean (geom. Mean) and geometric %CV (geom. %CV), except  $t_{max}$  which will only be presented with min, median, and max.
- Categorical variables: Categorical data will be summarized with the number of non-missing values and the frequency of each of the possible values. Percentages of subjects with each of the possible values will be calculated from the number of subjects in the corresponding analysis population, unless stated otherwise. Percentages will be presented to one decimal place, except 100% which will be displayed without any decimal places, or stated otherwise.

- The mean value will be presented one decimal place more than raw. The standard deviation will be presented two decimal places more than raw data, except %CV and geom. %CV will be presented with one decimal place. The minimum, maximum, and median values will be presented to the same precision as the raw data. A maximum of four decimal places will be presented.
- Some continuous variables may also be grouped into categorical levels and evaluated in frequency tables.
- The NCA parameters will not be reported to any greater precision than that of the observed concentration data. Default reporting in text and tables is 3 significant figures except for time related parameters. Time related parameters will be reported to two decimal places.

Subjects with protocol deviations/violations affecting PK/PD results will be determined prior to the database lock.

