#### **9.4.3 Safety Analyses**

All safety analyses will be performed on the Safety Population.

All safety data will be listed according to treatment group, subject number, and visit.

The AEs are defined in [Section 8.3.1](#). The DLAE are defined in [Section 4.6](#).

AEs will be coded using the Medical Dictionary for Regulatory Activities (MedDRA) Version 22. The number of AEs and incidence rates will be tabulated by preferred term and system organ class.

The AEs will be coded by maximum severity, relationship to study treatment, as SAEs or DLTs as needed, and will be categorized and tabulated for each treatment group (cohort).

DLAEs will be presented in the same manner as the AEs.

Incidence of injection site reactions will be summarized by treatment group, and if appropriate by assessment time.

All laboratory test results, vital signs measurements, ECG results, weight, and body mass index will be summarized for each treatment group using descriptive statistics at each visit for raw numbers and change from baseline. The incidence of treatment-emergent abnormal laboratory, vital sign, and ECG values will also be summarized using descriptive statistics.

For 12-lead ECG parameters (HR, PR, QRS, QT, QTcF), the 90 % confidence interval will also be presented for each parameter mean and change from baseline values. Outliers for QT and QTcF defined under outcome measures will be summarized using counts and percentages by treatment and sampling time, if appropriate and using subject-level maximum over time by treatment. The following categories will be presented by treatment and overall, for JK07:

- outlier QT and QTcF intervals (450-480 ms, 480-500 ms and >500 ms)
- change from baseline in QT and QTcF intervals (30-60 ms and >60 ms)

Additional corrections to QT may also be similarly analyzed. If relevant, analysis excluding ECGs capturing paced beats will be performed.

Abnormal findings on 12-lead ECG will be summarized by treatment using descriptive statistics.

All recorded ECGs will be interpreted on site and subsequently collected, digitized, and sent for central laboratory standardized measurements. The incidence (number of subjects and percent) of a confirmed positive ADA response will be summarized by treatment. The incidence of neutralizing anti-drug antibody response will also be summarized, if appropriate.

All data will be provided in data listings sorted by treatment group, subject number, and visit.

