## **B. Adverse Events**

An adverse event (AE) is defined as any untoward medical occurrence in a clinical study subject administered a pharmaceutical product, which does not necessarily have a causal relationship with the study IP. A treatment-emergent adverse event (TEAE) is defined as an AE that started or worsened in severity on or after the date of the IP administration (Day 1). All AEs will be coded using the Medical Dictionary for Regulatory Activities (MedDRA) Version 22.1 and will be summarized by System Organ Class (SOC) and Preferred Term (PT).

All adverse events will be graded using the Common Terminology Criteria for Analysis Events (CTCAE) Version 5.0, ranging from 1 to 5: Grade 1 (Mild), Grade 2 (Moderate), Grade 3 (Severe), Grade 4 (Life threatening or disabling), or Grade 5 (Death). If the grade is missing for a TEAE, the event will be counted as grade 3 in the summary tables.

Subjects will be observed for possible allergic reactions following the treatment and will be monitored for DLAEs throughout the study. All AEs, including SAEs, will be collected from the time of enrollment until 30 days after the treatment. Following the first 30 days, only SAEs that are at least possibly related to the treatment or study procedures will be collected.

An overall summary for subjects with AEs will be summarized by cohort (each dose level of JK07 and the placebo group pooled across all the treatment groups) including the following subsets. The number of events and subjects will be included.

- **AEs**
- **TEAEs**
- TEAEs related to study drug. This subset includes TEAEs with a drug relationship of “possibly related” and “definitely related”, or a missing drug relationship.
- Serious TEAEs
- Serious TEAEs related to study drug. This subset includes Serious TEAEs with a drug relationship of “possibly related” and “definitely related”, or a missing drug relationship.
- TEAEs leading to study drug permanent discontinuation
- TEAEs leading to study drug infusion interruption. This subset includes TEAEs with an answer “Yes” to the question “Was infusion interrupted?” on the Infusion Drug Administration form.
- Treatment-emergent infusion site reactions. This subset includes TEAEs with an answer “Yes” to the question “Was this an infusion site reaction?” on the AE form
- TEAES by maximum grade. Only present the number of subjects for this subset.

- **DLAEs**

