- DLAEs related to study drug. This subset includes DLAEs with a drug relationship of “possibly related” and “definitely related”, or a missing drug relationship.
- Serious DLAEs
- Serious DLAEs related to study drug. This subset includes Serious DLAEs with a drug relationship of “possibly related” and “definitely related”, or a missing drug relationship.
- DLAEs leading to study drug permanent discontinuation
- DLAEs leading to study drug infusion interruption. This subset includes DLAEs with an answer “Yes” to the question “Was infusion interrupted?” on the Infusion Drug Administration form.
- DLAEs with infusion site reactions. This subset includes DLAEs with an answer “Yes” to the question “Was this an infusion site reaction?” on the AE form
- **SAEs**

In addition, summary tables will present the number and percentage of subjects and events by treatment group and overall, ordered by System Organ Class (SOC), Preferred Term (PT), and by the following classes, using the Safety Evaluation Population:

- SAEs
- SAEs having Infusion Site Reaction
- TEAEs
- TEAEs leading to study drug infusion interruption
- TEAEs leading to study drug permanent discontinuation
- TEAEs related to study drug
- TEAEs having Infusion Site Reaction
- DLAEs
- TEAEs by maximum severity (i.e. by CTCAE grading)
- TEAEs by maximum relationship to study drug

The DLAEs will be summarized by SOC and PT for the DLAE Evaluation Population.

At each level of summary of subject, a subject will be counted once if he/she reported one or more events. Specifically:

- For summary of TEAEs by severity, a subject will be classified according to the most severe event.
- For summary of TEAEs by relationship to study drug, a subject will be classified according to the closest relationship.

- For summary of SAEs by outcome, a subject will be classified according to the worst outcome.

For summary of TEAEs by action taken with study drug, a subject will be classified as “Drug Permanently Discontinued,” “Dose Interrupted,” “Other Action,” or “Dose Not changed.”

All AEs will be presented in a by-subject listing, detailing in the verbatim term given by the investigator, PT, SOC, start date, end date or ongoing, severity, seriousness, outcome, relationship to the study drug, and action taken. Treatment-emergent infusion site reactions, TEAEs leading to drug permanently discontinuation, and TEAEs related to study drug, DLAEs, SAEs, and deaths will be presented in separate listings respectively.

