### **D. Vital Signs**

Vital sign parameters, including the weight, body temperature, heart rate, respiratory rate, and systolic and diastolic blood pressure, will be summarized using descriptive statistics by cohort at each visit, by treatment group (and placebo) and overall. Absolute values and changes from baseline will be presented.

Vital signs will also be presented in a by-subject listing, detailed in result, unit, CFBL.

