## **H. Incidence of Emergent Rhythm Abnormality (Arrhythmias)**

Based on the primary endpoint of rhythm abnormalities and available data, incidence of emergent rhythm abnormalities will be analyzed.

Subjects will be supplied with an e-Patch to monitor heart rhythm for continuous 14 days during the screening period. Clinically significant rhythm abnormalities during the screening period will result in exclusion from randomization on the basis of exclusion criteria 12 (page 37 of Protocol Amendment 3). Continuous telemetry monitoring will start as soon as practicable after hospital admission on Day 1 and prior to the treatment. It will continue until 48 hours after the end of study drug infusion on Day 3.

The percentage of emergent clinically significant arrhythmias detected by telemetry will be compared, both overall and on a per day basis following the administration (i.e. 0-24 hours and 24-48 hours), between each treatment group and placebo and will be presented in a summary table.

A listing will be generated for all subjects with incidence of rhythm abnormality.

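### The SAP defines no pooled JK07 group and drops, without declaring it, the protocol's JK07-only overall summary of QT/QTcF outliers; an all-JK07 column beside pooled placebo repairs both at no real cost

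*SAP*

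**What the plan says.** **Groups.** SAP V.M states: "Subjects who received placebo will be combined into one treatment group for purposes of analysis". It then lists five JK07 dose groups and one further group, "Placebo (corresponding to the pooled group of subjects receiving the placebo". No group combines the JK07 doses.

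**Overall.** The same section says "Results will be summarized by treatment and overall, where appropriate". The term recurs without a definition:
- SAP VII.B, adverse events by system organ class and preferred term: "summary tables will present the number and percentage of subjects and events by treatment group and overall".
- SAP VII.D, vital signs: "by treatment group (and placebo) and overall".
- SAP VII.C uses it for laboratory results, and VII.E and VII.I use it for medical history and medications.

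Two safety displays name no overall column. The adverse-event overview has "each dose level of JK07 and the placebo group pooled across all the treatment groups". The arrhythmia comparison in SAP VII.H is made "between each treatment group and placebo and will be presented in a summary table".

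**QT/QTcF outliers.** Protocol 9.4.3 is more specific: "The following categories will be presented by treatment and overall, for JK07". It also asks that outliers be summarized by each subject's maximum across time points. SAP VII.G tabulates the categories only per cohort at each sampling time. SAP I.B gives the SAP precedence over the protocol. The SAP's Changes from Protocol section declares one item, the absence of an abnormal vital-sign table.

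**The concern.** The introduction to SAP VII says placebo subjects are included so that background disease can be told apart from treatment effects. A column that combines both arms does not serve that purpose, and no adverse-event, laboratory, vital-sign, ECG or arrhythmia table is specified with the JK07 doses taken together. The only analysis that sets all JK07 subjects against placebo is the treatment indicator in the exploratory concentration-QT model (SAP IX.B).

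The QT/QTcF point is firmer because it does not depend on how overall is read. The protocol specified a JK07-only overall and a subject-level maximum for a component of a primary endpoint. The governing SAP carries over neither and does not say so.

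At stake is a single stated incidence for JK07 in a study whose individual dose groups hold only 3 to 7 subjects.

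**Working it through.** **Inputs.** A standard cohort has 1 JK07 sentinel plus 4 randomized 3:1 (SAP IV.D). An expanded cohort has 1 sentinel plus 8 randomized 6:2 (SAP IV.A). There are five cohorts, with up to seven possible. The plan's maximum reproduces: 7 × 9 = 63. The Safety Evaluation Population requires randomization (SAP V.K), and sentinels are not randomized (SAP IV.D), so counts without sentinels are given in brackets.

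| Design | JK07 | Placebo | JK07 per dose | Placebo share of a mixed total |
|---|---|---|---|---|
| Five cohorts of 5 | 20 (15) | 5 | 4 (3) | 5/25 = 20% (5/20 = 25%) |
| Five cohorts of 9 | 35 (30) | 10 | 7 (6) | 10/45 = 22% (10/40 = 25%) |
| Seven cohorts of 9 | 49 (42) | 14 | 7 (6) | 14/63 = 22% (14/56 = 25%) |

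**Effect of mixing.** Mixed rate = JK07 rate − placebo share × (JK07 rate − placebo rate). With assumed rates of 40% on JK07 and 10% on placebo:
- share 20%: 40 − 0.20 × 30 = 34.0%
- share 25%: 40 − 0.25 × 30 = 32.5%

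The sign reverses if the placebo rate is the higher one.

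**Precision for an event not seen.** One-sided 95% upper limit = 1 − 0.05^(1/n), assuming one common risk across the pooled doses.

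| n | Upper limit |
|---|---|
| 4 (3), one dose, standard cohort | 53% (63%) |
| 7 (6), one dose, expanded cohort | 35% (39%) |
| 20 (15), pooled | 14% (18%) |
| 35 (30), pooled | 8% (10%) |
| 49 (42), pooled | 6% (7%) |

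The chance of seeing at least one event at an assumed true rate of 10% is 1 − 0.9^n: 34% at n = 4, 88% at n = 20, 52% at n = 7 and 99% at n = 49.

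**Contrast with placebo.** The plan states no alpha or power. For scale, Fisher's exact test at an assumed two-sided 0.05, sentinels counted, has this power:

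| Assumed rates | Sizes | Pooled JK07 vs placebo | One dose vs placebo |
|---|---|---|---|
| 40% vs 10% | 20 or 4 vs 5 | 7.6% | 11.4% |
| 40% vs 10% | 49 or 7 vs 14 | 53.3% | 26.3% |
| 60% vs 10% | 20 or 4 vs 5 | 48.7% | 32.3% |
| 60% vs 10% | 49 or 7 vs 14 | 94.5% | 59.1% |

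**QT/QTcF counts.** Protocol Table 2 schedules eight post-dose ECG times through 48 hours (end of infusion, 0.5, 1, 2, 4, 8, 24 and 48 hours). Suppose one JK07 subject exceeds a limit at each time. Among 20 JK07 subjects this could be the same subject throughout (1/20 = 5%) or eight different subjects (8/20 = 40%). Tables per time point cannot tell these apart; a subject-level maximum can.

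**The case against.** **Overall is undefined, not defined as mixed.** A reader might infer that the SAP fixes overall as JK07 plus placebo. It does not. The wording is qualified, the table shells are a separate document that may settle the columns, and Protocol 9.4 uses almost the same general sentence. The protocol limits overall to JK07 only for the QT/QTcF categories. This stands: a mixed column is the plain reading, supported by the SAP V.M rule that percentages use the whole analysis population, but it is not stated.

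**Mixing need not understate the JK07 rate.** This also stands. Understatement requires a lower placebo rate, and patients with heart failure have background events.

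**Pooled counts can be added up.** Dose columns are disjoint, so subject and event counts for adverse events can be summed. Medians of laboratory or vital-sign changes cannot be rebuilt that way, and neither can the number of subjects ever beyond a QT limit. SAP VII.G does plan a listing of QT/QTcF category records, so that number could be extracted by hand, but no summary table gives it.

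**Pooling has its own dilution.** The five planned doses span 1.08/0.03 = 36-fold, and Protocol 4.3 says the lowest was chosen as unlikely to have a clinical effect. This is a good reason to keep the dose columns. It is not a reason to omit a pooled one: the protocol itself chose pooling for QT, and Protocol 4.2 describes the monkey QT, troponin and myocardial findings without a dose trend.

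**Conclusion.** The point holds as a low-cost improvement. Two findings are secure: the SAP names no all-JK07 group and never limits overall to JK07, and the protocol's JK07-only overall and subject-level maximum for QT/QTcF outliers are missing from the SAP without being declared. That placebo would make up 20% to 25% of an overall column depends on the plain reading of an undefined term.

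The benefit is precision in JK07 incidence, on the assumption of a common risk across doses. A reader might go further and take pooled JK07 against pooled placebo as the one comparison of useful size. The documents do not support that. No hypothesis test or size criterion is set, and the placebo group stays at 5 to 14. In the initial 20 vs 5 design, pooling gives no more power than a single dose at an assumed 40% vs 10%. It helps there only at larger differences, and more clearly once cohorts are expanded. The pooled column supplements the by-dose display and does not replace it.

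**What to change.** 1. In the adverse-event, laboratory, vital-sign, ECG and arrhythmia tables, add an all-JK07 column beside pooled placebo and keep every dose column.
2. Restore the JK07-overall QT/QTcF outlier summary, including each subject's maximum across time points, or list its removal under Changes from Protocol.
3. Define overall for each table. A total over both arms may stay in the medical history and medication tables.
4. State whether sentinel subjects count in the safety denominators.

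The cost is a SAP text edit and revised table shells. No new data, visits or subjects are needed.

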t Subjects who do not complete all required visits or withdraw from the study early are required to complete End-of Study/Early-Termination assessments (Day 180) as described in [Section 7.2](#).

u Randomization will occur approximately one to two weeks prior to scheduled date of IP infusion, at the time of scheduling the inpatient admission, and will trigger shipment of IP and administration kit to site. See [Section 6.3](#) for description of randomization procedures.

v Study visits on Day 11 and Day 22 may be conducted remotely at the discretion of the Principal Investigator based on their local risk assessment, in which case, the requirement for vital signs, ECGs, physical examination, and PK blood draws will be waived. The procedures will be performed as per the SoA if the visit takes place at the clinical site.

NOTE: See [Appendix 3 Clinical Laboratory Tests](#), [Table 13](#) for a complete list of protocol-required laboratory assessments that will be performed; see [Table 14](#) for a list of safety laboratory assessments (and assessment timepoints) that will be performed by the local laboratory; see [Table 15](#) for a list of safety and exploratory biomarker assessments that will be performed by a central laboratory.

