#### **9.4.5 Missing Data**

Data from subjects who withdraw from the study, including AEs and any follow-up, will be included in the analyses of all outcomes.

Missing data will be excluded from the analyses. No imputation will be performed, unless specified.

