## **B. Disposition**

The summary table of subject disposition will include all screened subjects and display the following by treatment (if applicable):

- Number of subjects who screened
- Number and percentage of subjects who failed screening with the failed inclusion/exclusion criteria as the reason of screen failure
- Number of randomized subjects
- Number and percentage of randomization failures, using the number of randomized subjects as denominator for the percentages. Randomization failure subjects are those that passed initial screening assessments and were randomized into the trial but failed out on Day 1 due to any Day 1 labs/assessments making them ineligible (e.g., they had become pregnant, lab values were unacceptable per exclusion criteria, any morning test results were exclusionary).

Subjects who discontinued the study with discontinuation reason = “Randomization Failure” on the Study Discontinuation Form will be counted as randomization failures in the summary.

- Number and percentage of subjects in each analysis population, using the number of randomized subjects as denominator.
- Number and subjects discharged later than Day 3.
- Study completion status (completed or permanently discontinued). List the number and percentage of subjects for each reason of discontinuation, using the number of randomized subjects as denominator for the percentages.
- Number of days in the study among the randomized subjects, calculated as: End of Study Date (completion or discontinuation) – IP administration date + 1.

The following termination reasons as recorded on the End of Study form will be considered:

- Adverse event
- Death
- Lost to follow-up
- Physician decision
- Study terminated by sponsor
- Subject non-compliance/protocol violation
- Withdrawal of consent

A listing will present subject enrollment, with the protocol version for which subject was enrolled, and the inclusion in each analysis population.

A separate listing by subject will display the details of screen failure reason of each subject.

A by-subject listing will display subject disposition. All randomized subjects will be included.

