#### **G. Electrocardiograms (Digital 12-Lead Triplicate ECGs)**

Each subject will receive triplicate, twelve-lead ECG evaluations including HR, PR, QRS, QT (uncorrected), QTcF (corrected), and an overall evaluation of normality and clinical significance during screening and starting on Day 1 following admission to the hospital. ECG data will be collected, reviewed and analyzed by a Central Reader and the Principal Investigator. Findings identified by the Central Reader will be listed only for the concerned subjects.

The triplicate measurements of each subject at each timepoint will be averaged before summary. The observed values and mean CFBL of these ECG measurements will be summarized by cohort at each timepoint using descriptive statistics including 90% confidence interval of the mean. The overall ECG evaluation results, alone with shift from baseline (from abnormal to normal, or from normal to abnormal) will be summarized in a separate table by each treatment cohort and aggregated placebo at each visit. Results collected by the Central Reader and the Principal Investigator will be displayed separately.

Categories of QT and QTcF intervals (431-450 ms and >450 ms for males, and 451-470 and >470 ms for females) and CFBL in QT and QTcF intervals (30-60 ms, and >60 ms) will be summarized using counts and percentages by cohort and sampling time. Additional corrections to QT may be analyzed in a similar way. Results collected by the Central Reader and the Principal Investigator will be displayed separately.

A significant proportion of HFrEF patients with pre-existing implanted functional atrio-ventricular (A-V sequential) pacemakers and cardiac resynchronization devices (CRT), may be unevaluable with respect to QT/QTc analysis due to the inherently prolonged and fixed QRS configuration. The presence of these devices, which include defibrillators, is not considered an increased safety risk.

The electrocardiogram analysis will be conducted by cohort in the following two groups and presented separately:

- All subjects
- Subjects not having pacemakers identified by the contents of ECG overall evaluation. If none of the ECG evaluations have the word “pace” or “paced” or “pacemaker” or “electronic” or “electronically” or “resynchronization” or “CRT” for a subject, the subject is considered not to have a pacemaker or CRT (cardiac resynchronization therapy).

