## **XI. Immunogenicity Assessments**

The analyses described in this section will be performed at CR Medicon.

Subjects who received placebo will be combined into 1 treatment group for purposes of analysis.

Serum samples for the antibody assays will be collected at Day 1, 4, 7, 15, 30, 90 and EOS/180. Additionally, subjects who do not complete all required visits or withdraw from the study early are required to complete End-of Study/Early-Termination assessments. The serum samples for antibodies will be assayed for neutralizing antibodies.

Immunogenicity will be evaluated using descriptive statistics. The number and percentage of subjects for ADA and neutralizing antibodies results will be summarized by treatment at scheduled time point as well as all post-baseline visits. Percentages for the neutralizing antibody result are based on the number of positive ADA results at that visit. ADAnalysisA titers of subjects who becomes antibody positive will be summarized by treatment and cohort as received along with nominal collection time. Summary statistics including n, min, max, mean and median will be calculated. In addition, incidence of early and delayed-type hypersensitivity responses will be summarized by ADA results (positive or negative) and by treatment.

Antibody information of subjects will be presented in the form of data listings.

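### The SAP's default denominator dilutes by-visit ECG, laboratory-shift and ADA percentages whenever results are missing; these tables should use the subjects measured at that time

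*SAP*

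**What the plan says.** SAP V.M (Data Display Characteristics) gives the general rule: "Percentages of subjects with each of the possible values will be calculated from the number of subjects in the corresponding analysis population, unless stated otherwise". The sentence before it says what else is shown: "Categorical data will be summarized with the number of non-missing values and the frequency of each of the possible values".

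The SAP departs from the default in two places:
- Disposition (SAP VI.B) works out its percentages "using the number of randomized subjects as denominator for the percentages".
- Immunogenicity (SAP XI) gives neutralizing antibodies a visit-specific base: "Percentages for the neutralizing antibody result are based on the number of positive ADA results at that visit".

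It does not depart from the default for these tables:
- QT and QTcF categories, which "will be summarized using counts and percentages by cohort and sampling time" (SAP VII.G).
- Shifts in the overall ECG evaluation by visit (SAP VII.G) and shifts in laboratory normality (SAP VII.C).
- ADA status: "The number and percentage of subjects for ADA and neutralizing antibodies results will be summarized by treatment at scheduled time point" (SAP XI).

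On missing data, Protocol 9.4.5 says "Missing data will be excluded from the analyses". SAP V.D does not impute missing safety data and shows them as missing. SAP I.B gives the SAP precedence over the protocol and places the table shells in a separate document.

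Gaps are foreseen. Under Protocol Table 1, footnote v, if a Day 11 or Day 22 visit is held remotely, "the requirement for vital signs, ECGs, physical examination, and PK blood draws will be waived". Protocol 7.2 allows withdrawal at any time during follow-up, which runs to Day 180.

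**The concern.** A by-visit percentage is normally read as the share of subjects assessed at that visit who had the finding. Under the default it is the share of the whole analysis population, assessed or not. When results are missing, the printed figure falls below the share among those assessed.

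For safety findings the error runs towards reassurance. QT/QTcF outliers, laboratory changes and anti-JK07 antibodies all belong to the primary endpoints. Dose groups are small, so one missing result moves a percentage noticeably. The dilution depends on each group's own missing fraction, so unequal missingness also alters the comparison of a JK07 dose with pooled placebo.

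SAP XI is also uneven within itself: neutralizing-antibody percentages use a base specific to the visit, while ADA percentages in the same section fall back on the population count.

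**Working it through.** The plan states no percentage, missing-data rate or power figure on this point, so there is no figure to reproduce. The check is direct arithmetic.

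**Inputs from the documents.** Cohorts run from 5 subjects (1 sentinel plus 3:1) to 9 (1 sentinel plus 6:2). A JK07 dose group therefore has N = 1 + 3 = 4 to 1 + 6 = 7 with the sentinel, or 3 to 6 without. Pooled placebo has N = 5 × 1 = 5 (five unexpanded cohorts) up to 7 × 2 = 14 (seven expanded cohorts).

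**Assumed inputs.** x = 1 subject with the event at a visit; m = 1 or 2 subjects with no result at that visit.

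**Formulas.**
- SAP default: x/N
- Among those measured: x/n, with n = N − m
- Full-data range: from x/N (no missing subject had the event) to (x + m)/N (all did)
- Sum of the category percentages under the default: (N − m)/N

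| Group | N | m | x/N | x/n | Full-data range | Categories sum to |
|---|---|---|---|---|---|---|
| JK07, unexpanded | 4 | 1 | 25.0% | 33.3% | 25.0–50.0% | 75.0% |
| JK07, unexpanded | 4 | 2 | 25.0% | 50.0% | 25.0–75.0% | 50.0% |
| JK07, expanded | 7 | 1 | 14.3% | 16.7% | 14.3–28.6% | 85.7% |
| JK07, expanded | 7 | 2 | 14.3% | 20.0% | 14.3–42.9% | 71.4% |
| Placebo, 5 × 1 | 5 | 1 | 20.0% | 25.0% | 20.0–40.0% | 80.0% |
| Placebo, 7 × 2 | 14 | 1 | 7.1% | 7.7% | 7.1–14.3% | 92.9% |

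With m = 0 or x = 0, x/N and x/n are equal.

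**Where the missing subject goes.** Take N = 4, x = 1, m = 1. The event category prints 1/4 = 25.0% and the event-free category 2/4 = 50.0%, a total of 75.0%. The missing subject is in neither category, and both percentages are diluted.

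**Effect on a contrast.** One missing result with one event costs 1/3 − 1/4 = 8.3 points in a JK07 group of 4, but 1/13 − 1/14 = 0.5 points in a placebo group of 14. For unequal missingness, take JK07 with N = 4, x = 1, m = 1 and placebo with N = 5, x = 1, m = 0. The default shows 25.0% − 20.0% = 5.0 points; among those measured the difference is 33.3% − 20.0% = 13.3 points.

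**Which visits are exposed.** Table 1 schedules an ECG on Day 11 but none on Day 22, and no laboratory panel or ADA sample on either day. For the tables at issue, the remote-visit waiver therefore affects only the Day 11 ECG. For laboratory and ADA tables, the foreseeable gaps come from early withdrawal and missed samples.

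**The case against.** A reader might infer three stronger things, none of which the documents support.

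- **That every categorical percentage is affected.** The rule is a default. Disposition and neutralizing antibodies have their own stated bases, and for AE, SAE and other whole-study subject-level incidence the population count is the usual denominator.
- **That missing subjects are counted as event-free.** Nothing assigns a missing result to normal or negative, and SAP V.D leaves it missing. The event percentage is numerically the same as if they had been so counted, but the event-free percentage is diluted too and the shortfall from 100% is visible.
- **That x/n is the true rate and x/N a known understatement of it.** This holds only if missingness is unrelated to outcome. If two of four results are missing and neither subject had the event, 25.0% is right and 50.0% is wrong.

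Other points on the plan's side also have force:
- The non-missing count is displayed, and by-subject listings cover ECG, laboratory and antibody data.
- Protocol 9.4.5 does not itself set a denominator, and Protocol 9.4 leaves missing-data procedures to the SAP. The tension is real but is not a flat contradiction.
- The most intensive ECG sampling is inpatient. Early leavers are asked to complete the end-of-study assessments. ADA is also summarised over all post-baseline visits, so a missed late sample does not erase an earlier positive.
- The study tests no hypotheses, and the separate table shells, not available here, may set by-visit denominators.

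These points limit the consequence without removing it. The printed percentage is the one likely to be quoted, and the SAP text that governs the analysis gives the diluted base.

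**Conclusion.** The point holds in a limited form. As written, the SAP applies the population count to by-visit and by-sampling-time QT/QTcF categories, ECG and laboratory shifts, and ADA status at scheduled time points. Where results are missing, the event percentage it prints is the lower bound of what the data allow.

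In the smallest JK07 group (N = 4, sentinel included), one event and one missing result give a gap of 8.3 points; in a pooled placebo group of 14 the gap is 0.5 points. Both rest on assumed event and missing counts. The documents state no missing-data rate, so the size in this trial cannot be fixed, and it is zero at any visit with complete data.

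This is a reporting convention worth correcting because the correction is cheap. It does not show that any conclusion of the study would change.

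**What to change.** In SAP V.M, add that percentages in by-visit tables, by-sampling-time tables and shift tables use subjects with a non-missing result at that time, and for shifts also a non-missing baseline. Show them as x/n alongside N.

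Keep N for AE, SAE and other whole-study subject-level incidence tables, and keep the stated bases for disposition and neutralizing antibodies. Name the analysis population for ADA in SAP XI, which currently gives none, and bring the table shells into line.

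The cost is a sentence or two and a shell edit. The downsides are that denominators will vary across visits, and that x/n is unbiased only if missingness is unrelated to outcome. Showing n and N together lets the reader see how much is missing and work out the possible range.
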